Due to tubular re-absorption of radiolabelled peptide agents, radiation-induced kidney disease is the main safety concern for PRRT. Both, acute renal toxicity with increased serum creatinine and long-term nephropathy with creatinine clearance loss (CCL) of 5 to more than 10% per year (Bodei et al., 2008) may occur. Nephropathy is reported to be more pronounced in patients with renal risk factors (arterial hypertension, diabetes mellitus), pre-existing renal impairment or those who have received earlier nephrotoxic treatment modalities (chemotherapy, local EFR, prior PRRT) (Bodei et al., 2008).

All patients in the above-mentioned academic study were pre-treated with a nephroprotective amino acid solution, administered IV starting 30 min to and lasting 3 – 4 h after the start of the PRRT infusion, according to current guidelines (Bodei et al., 2013; Zaknun et al., 2013; IAEA 2013). Such regimen has been shown to decrease the renal absorbed radiation dose by 50% without reducing the tumour uptake (Rolleman et al., 2010). Using this regimen, no clinically relevant nephrotoxicity following PRRT with  $^{177}\text{Lu}$ -edotreotide was observed, as evaluated by extended renal function testing (glomerular filtration rate [GFR], creatinine, tubular extraction rate [TER],  $\text{K}^+$  and BUN).

In the context of the planned trial, a similar nephroprotective regimen will be used. In addition, patients with impaired renal function ( $\text{GFR} < 60 \text{ mL/min/1.73 m}^2$ ), or ill-controlled renal risk factors will be excluded from participation. As a further safety measure, absorbed organ doses to the kidneys will in principle be restricted to  $\leq 23 \text{ Gy}$ , as per current guidelines on PRRT (Bodei et al., 2013; Zaknun et al., 2013; IAEA 2013). If the predicted absorbed dose to the kidneys likely exceeds 23 Gy upon administration of the next PRRT cycle, additional measurement of renal function must be performed. In case this pre-therapeutic TER ( $^{99\text{m}}\text{Tc}$ -MAG3 renal scintigraphy) is  $>50\%$  of baseline, dosing can be continued. However, the absorbed dose is not allowed to exceed 29 Gy, as suggested by Konijnenberg et al. (2007).

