#### 5.4.1.1 Absorbed Dose from Lu-Edotreotide PRRT to the Kidneys

Traditionally, an absorbed dose (AD) to the kidneys, not exceeding 23 Gy has been recommended to effectively avoid radiation-induced toxicity to the kidneys (IAEA PRRNT guideline 2013). Current dosimetric studies and clinical observations demonstrate, however, that an AD of 23 Gy does not correlate with kidney toxicity in PRRT, and that radiation tolerance of the kidneys for PRRT is actually higher than 23 Gy (Barone et al., 2005; Strosberg et al., 2017). Absorbed doses to kidneys have been described to vary considerably between patients, while at the same time variation of AD does not predictably correlate with body weight (Barone et al., 2005; Schuchardt et al., 2013, Strosberg et al., 2017) (see Section 3.4).

For safety reasons, therefore, AD to kidneys will be measured in all PRRT patients after their 1st PRRT cycle in this study. The absorbed dose to the kidneys (in Gy/GBq) is calculated based on AD to kidneys from Lu-edotreotide activity (in GBq) administered during the first cycle. From this, the cumulative AD to kidneys (in Gy) can be estimated for the cumulative activity dose (GBq) administered during the study, individually for each patient. If it can be anticipated that according to the individual AD per GBq of Lu-edotreotide, the traditional limit of a total of 23 Gy would be exceeded in a subsequent treatment cycle, no further treatment cycle will be administered, unless a) clinically relevant tubular renal dysfunction (see below) can be excluded, and b) the investigator considers it in the best interest of the patient to undergo a next cycle.

A PRRT cycle leading to transgression of an AD to kidneys of >23 Gy may only be administered on condition that a) the TER ( $^{99m}\text{Tc}$ -MAG3 renal scintigraphy) determined before this cycle, is >50% of the value at baseline (a value not associated with GFR changes), and b) and that the resulting AD to kidney will not exceed a maximum of 29 Gy (Konijnenberg et al., 2007; Bodei et al., 2013; Barone et al., 2005; Strosberg et al., 2017).

#### 5.4.1.2 Eligibility for Continued Administration of $^{177}\text{Lu}$ -edotreotide after Cycle 1

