#### **7.3.1.4 Day 3 (only $^{177}\text{Lu}$ -edotreotide group)**

##### Prior to Imaging:

- Vital signs 72 – 96 h ( $\pm$  3 h) post start of infusion
- 12-lead ECG 72 - 96 h ( $\pm$  3 h) post start of infusion
- Concomitant medications and SSA medications continuously
- Adverse events continuously

Patients randomised to  $^{177}\text{Lu}$ -edotreotide group will receive bi-weekly haematology controls for 8 weeks following  $^{177}\text{Lu}$ -edotreotide administration at week 2, 4, 6, 8 post-PRRT (general practitioner acceptable).

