3.1 General Study Design and Plan

Phase: III, multi-centre

Study configuration and experimental design: confirmatory, prospective, parallel group

Type of control: active drug

Blinding: open-label

Treatment assignment: 300 GEP-NET patients randomised in a 2 : 1 fashion to receive either

- PRRT with ^{177}Lu -edotreotide consisting of a maximum of four cycles (7.5 ± 0.7 GBq ^{177}Lu -edotreotide, each), administered as IV infusion at 3-monthly intervals for 9 months, or until diagnosis of progression (200 patients), or
- 10 mg everolimus (Afinitor®) daily, administered orally as a tablet (100 patients).

Duration: Baseline: day -90 to -1

Randomisation: day -28 to -1

Treatment and study procedures: month 0 to 30, or until progression or withdrawal – whichever occurs earlier

EOS: month 30 or at progression or drop-out - whichever occurs earlier

Collection of survival and local disease progression data as well as information on further tumour treatments will be continued after EOS during the long-term follow-up.

Please refer to Section 3.1 of the current protocol for more details.

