3.4.3.2 Safety and Tolerability Parameters

- a) Tubular extraction rate (TER), percentage depart from baseline value
- b) Glomerular filtration rate (GFR), percentage depart from baseline value
- c) Renal volume (V_{kidney}), percentage depart from baseline value
- d) Frequency of occurrence and severity of abnormal findings in safety investigations (vital signs, 12-lead ECG, clinical laboratory, adverse events)

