5.3 General Statistical Methods

Statistical analyses will be performed after the data base was appropriately locked.

All data from the CRF and other study and measurement documents will be analysed. Continuous parameters will be summarised using descriptive statistics (number, mean, standard deviation, minimum, median, maximum) and categorical parameters using frequency tables. Corresponding 95% confidence intervals will be presented additionally where meaningful.

Statistical hypothesis testing of the primary variable and the key secondary variables will be performed maintaining an overall type I error (alpha) of 5% (two-sided).

Multiplicity will be accounted for by adhering strictly to the described interim analysis and hierarchy testing plan with regard to the primary and the key secondary endpoints (see Section 5.7).

Exploratory statistical hypothesis tests will be used at a significance level of 0.05 (two-sided) considered at a purely descriptive level.

Withdrawals and protocol deviations will be listed. Missing data that cannot be obtained will not be substituted, unless stated otherwise (See Section 5.5). A given data set entry is presumed to be an outlier if the value is evidently contrary to generally accepted data. Such occurrences will be recorded. Results from analyses excluding outliers may be explored by comparing results based on the complete data set, differences will be discussed.

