Time to HRQL deterioration will be calculated as the time from randomization to the first deterioration for the same domain. Patients with no deterioration are censored at the last adequate HRQL assessment date. Patients with no baseline and/or no follow-up are censored at randomization.

For each domain, a Kaplan-Meier plot will be produced showing time to event by treatment arm and used to generate a point estimate of the median time to event with corresponding 95% confidence interval (CI).

The stratified log-rank test will be used to compare the time to event in the two groups. The hazard ratios (HR) and corresponding 95% CIs will be estimated from a Cox proportional hazards model including randomized treatment as a factor.

For sensitivity analysis purposes, the p-value using a log-rank test not stratified on randomization stratification factors will also be computed as well as the corresponding hazard ratio (Cox model adjusting for the same factors).

Subgroup and/or multivariate Cox model analyses can be performed as deemed appropriate to explore the impact of co-variables on the HRQL results.

10 Dosimetry

Time activity curves of target organs and tumour lesions will be presented.

Descriptive statistics of target organ and tumour lesions absorbed doses in Gy/GBq will be tabulated by cycle (D1 for all patients, D2-4 for sub-study A patients). A summary of the mean absorbed dose and SD (in Gy/GBq and in Gy for 7.5 GBq) will also be presented by target organs and by cycle. The estimated extrapolation of the cumulative absorbed dose to target organs and tumour lesions will be summarised for a theoretical full course 4 doses of 7.5GBq (i.e. 30GBq).

The association between absorbed dose of ^{177}Lu -edotreotide in the tumours and RECIST 1.1 response will be explored, as well as the association between bone marrow absorbed dose and highest CTCAE haematological toxicities (AEs and labs) or kidney absorbed dose and highest CTCAE kidney toxicities (AEs and labs). Association between baseline kidney function impairment and organ dosimetry will also be explored based on baseline eGFR (i.e. classified as <15, [15,30[, [30,45[, [45,60[, [60,90[, ≥ 90 or less categories in case of too low sub-group sample sizes).

Sub-study A and B:

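### SAP section 10 relates kidney absorbed dose only to the highest CTCAE grade; relating it also to the percent change in TER and eGFR already collected would recover power if graded renal toxicity is uncommon

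*SAP*

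**What the plan says.** SAP section 10 (Dosimetry) plans to explore two dose-toxicity associations. For the kidney it names "or kidney absorbed dose and highest CTCAE kidney toxicities (AEs and labs"; for the marrow, "as well as the association between bone marrow absorbed dose and highest CTCAE haematological toxicities (AEs and labs". It names no test, model or effect size. SAP section 5.3 sets the status of any such test: "Exploratory statistical hypothesis tests will be used at a significance level of 0.05 (two-sided) considered at a purely descriptive level".

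Continuous measures of the same organs are collected:

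- **Kidney.** SAP section 3.4.3.2 lists TER and GFR as safety variables, for example "Glomerular filtration rate (GFR), percentage depart from baseline value". Protocol section 8.3.9 schedules TER at baseline and 6-monthly, and GFR at baseline and 3-monthly.
- **Blood counts.** Protocol section 7.3.1.4 requires "bi-weekly haematology controls for 8 weeks following" each administration, and section 3.1 says the same for D1 to D4.

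SAP sections 8.4 and 8.5 summarise these values by visit and treatment arm. In SAP Table 6, which lists the laboratory parameters to be graded, creatinine is the only measure of renal function; TER and GFR do not appear. Section 10 does look at baseline eGFR category against organ dosimetry, but that asks whether starting function affects dose, not whether dose affects later function.

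On numbers, Protocol section 5.4.1.1 states that "AD to kidneys will be measured in all PRRT patients after their 1" (the quote stops at the superscript; it means the first PRRT cycle), and SAP section 3.1 plans the PRRT arm as "or until diagnosis of progression (200 patients), or" the comparator. Marrow dose comes only from Sub-study C, with 20 patients.

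**The concern.** Absorbed dose is continuous, and so are TER and eGFR. Collapsing the outcome to the highest grade puts every patient without a graded event into one tied category. If that category holds most of the arm, an association of moderate size is likely to be missed.

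TER deserves particular attention. Protocol section 5.4.1.1 makes TER relative to baseline a condition for any cycle that takes kidney dose above 23 Gy, yet the SAP never analyses TER against absorbed dose. The same section says that 23 Gy does not correlate with kidney toxicity in PRRT. An uninformative null result on the grade scale would sit beside that statement, although data for a more informative analysis exist for the whole arm.

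**Working it through.** The documents state no power, effect size or test for this analysis, so there is no planned figure to reproduce. The check compares the two outcome scales under stated assumptions.

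**Inputs from the documents.** Kidney: n = 200 (planned PRRT arm). Marrow: n = 20. Two-sided 5% level.

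**Assumptions not in the documents.** Correlation r between dose and functional change; the share of patients with any grade of 1 or more; n = 150 as a lower kidney sample size to allow for non-evaluable patients.

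**Step 1: continuous outcome, Fisher z approximation.** Power = Φ(atanh(r)·√(n−3) − 1.96).

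- Kidney, n = 200, r = 0.2: 0.2027 × √197 = 2.845; 2.845 − 1.96 = 0.885; Φ = 81%.
- Smallest r with 80% power is tanh((1.96 + 0.842)/√(n−3)). For n = 200: tanh(2.802/14.04) = 0.20. For n = 20: tanh(2.802/4.123) = 0.59.

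**Step 2: same test on both scales, by simulation.** Dose and latent functional change were drawn from a bivariate normal distribution with correlation r. The change was tested by Spearman correlation with dose, once as the continuous value and once cut into ordered grades (about 4,000 replicates per setting). Using one test throughout matters. Pearson on the continuous value against Spearman on grades (81% against 64% in the first row below) would credit part of the gain to the change of test.

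Kidney, n = 200, r = 0.2, continuous outcome about 78%:

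| Patients with any grade | Example split, lowest grade first (%) | Power on highest grade |
|---|---|---|
| 40% | 60/30/8/2 | 64% (66% with 60/25/10/5) |
| 20% | 80/15/5 | 50–52% |
| 10% | 90/8/2 | 36–38% |
| 5% | 95/4/1 | 25–26% |
| widely spread | 30/35/25/10 | 73% (74% with 20/30/30/15/5) |

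The loss is therefore 78 − 64 = 14 points with 40% graded, 78 − 25 = 53 points with 5% graded, and about 5 points when grades are spread.

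**Step 3: sensitivity, kidney.**

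- n = 200, r = 0.3: continuous 98–99%; grades 95%, 84%, 69% and 50% with 40%, 20%, 10% and 5% graded.
- n = 150, r = 0.2: continuous 64–66%; grades 53%, 39%, 29% and 20%.

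**Step 4: marrow, n = 20.** At r = 0.3 the continuous outcome has only 22–23% power, and the grade outcome 18–19% with 40–50% of patients graded. At r = 0.5 the continuous outcome has 56–59%, and the grade outcome 46% with 40% graded and 33% with 20% graded. Grading costs something, but even the continuous scale needs r of about 0.59 for 80% power.

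**Step 5: which dose variable.** Protocol section 3.4 reports earlier kidney doses with mean 0.6 and range 0.3–1.6 mGy/MBq. At 30 GBq that is 0.3 × 30 = 9 Gy, 0.6 × 30 = 18 Gy and 1.6 × 30 = 48 Gy. Section 5.4.1.1 limits delivered dose to 23 Gy, or at most 29 Gy, and 29/30 = 0.97 mGy/MBq. Whether later cycles are given also depends on TER (5.4.1.1) and on creatinine and eGFR (5.4.1.2, 5.4.3.2). Cumulative delivered dose is therefore truncated and depends partly on the outcome. The cycle 1 value in Gy/GBq is measured before any of those decisions.

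**The case against.** Several points on the other side are sound.

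- **Conditional loss.** A reader might infer that the planned analysis has little power in general. The documents do not support that: they give no grade distribution, and with at least 40% of patients graded the grade scale keeps about 95% power at r = 0.3, n = 200.
- **The earlier study.** A reader might take "no clinically relevant nephrotoxicity following PRRT with" the study drug (Protocol section 1.3) as proof that grades will be sparse. That statement rests on extended renal function testing that included GFR and TER, so it does not show how patients would be graded. Nor does it support any particular dose-function correlation.
- **Marrow.** A reader might blame the grade scale for a weak marrow analysis. Step 4 shows that the sample size is the main limit. SAP section 11 justifies the 20 patients for describing pharmacokinetics, with no comparisons intended.
- **Status.** The SAP promises exploration and makes no confirmatory claim. The dose limits rest on cited guidelines and studies, not on this analysis, so misuse of a null result is a possibility and not a plan. CTCAE is also the trial's toxicity scale throughout, so using it is not a mistake.
- **Model.** The simulation gives both scales the same latent correlation. It ignores the dose cap and the fact that the highest grade also draws on adverse events and the worst value over follow-up.
- **Unseen material.** The table and listing tracker attached to the SAP is not available and might contain more.

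These points set the size and severity of the finding. They do not change the fact that the SAP text relates kidney dose to the grade alone while richer measures of the same organ are in hand.

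**Conclusion.** The point holds for the kidney as an optional improvement. The planned outcome is coarser than the data allow, and the cost in power ranges from about 5 points (grades widely spread) to about 53 points (5% of patients graded) at r = 0.2 and n = 200. The correlation and the grade splits are assumptions, and the cap on delivered dose would weaken any association on either scale. For the marrow, a continuous outcome is somewhat more informative, but no choice of scale makes 20 patients adequate for testing an association. No confirmatory conclusion of the trial is affected.

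**What to change.** In SAP section 10:

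1. **Kidney, main analysis.** Regress percent change from baseline in eGFR, and separately in TER, on kidney absorbed dose. Use a repeated-measures model adjusted for the baseline value, and report slopes with 95% confidence intervals. Repeated measures use all available visits, which matters because patients leave the study at progression (Protocol section 4.6).
2. **Dose variable.** Use cycle 1 absorbed dose in Gy/GBq as the main variable and delivered cumulative Gy as a supporting one. State the reason: the cumulative dose is capped and depends on interim renal function.
3. **Grades.** Keep the highest CTCAE grade against dose as a supporting description.
4. **Marrow.** Add marrow dose against log(nadir/baseline) of the blood counts, as estimates with confidence intervals and without a test-based conclusion. State that n = 20 is the main limit and that r of about 0.59 would be needed for 80% power.

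The cost is SAP wording and a little programming on data already collected, with no new visits or samples. The downside is that results on a functional scale still need the grade table beside them for clinical reading. The change should be made before analysis: under SAP section 16, analyses added without amending the protocol and SAP count as post hoc.

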17.1 Study Objectives Rollover Post-Treatment Extension Study

The objective of the rollover post-treatment extension analysis is to assess the safety, tolerability, and efficacy of ^{177}Lu -edotreotide PRRT in patients who received everolimus in the main study and discontinued treatment due to tumour progression.

17.2 Study Endpoints of Rollover Post-treatment Extension Analysis

17.2.1 Efficacy Endpoint

The efficacy endpoints in rollover study include Rollover Progression-free survival (Rollover PFS), Rollover overall survival (Rollover OS), Rollover Objective Response Rate (Rollover ORR), Rollover Disease control rate (Rollover DCR), Rollover Disease control rate (Rollover DCR), Rollover Duration of Response (Rollover DoR) and Rollover Duration of Disease Control (Rollover DDC).

Imaging for the assessment of PFS (using RECIST 1.1) will be performed and evaluated at the study centre according to local standards. RECIST 1.1 baseline must be reset at rollover post treatment extension entrance.

17.2.2 Safety and Tolerability Endpoint

General safety parameters include frequency of occurrence and severity of abnormal findings in safety investigations (physical examination, vital signs, ECG, $^{99\text{mTc}}$ -MAG3 renal scintigraphy, clinical laboratory tests), AEs, and concomitant medication.

17.3 Study Design of Rollover Post-treatment Extension Study

17.3.1 Enrolled Population

All patients participating in the main study in France who meet the eligibility criteria for the rollover extension are planned to be enrolled. Enrollment into the rollover extension will occur within 3 months of a patient's discontinuation from everolimus treatment in the main study. Patients who enroll in the rollover extension may have their early withdrawal visit procedures from the main study and rollover extension visit procedures done on the same day.

17.3.2 Study Duration of Rollover Post-treatment Extension Study

Patients in the rollover extension may receive up to a maximum of 4 cycles of ^{177}Lu -edotreotide. Each cycle will be administered as an IV infusion given 90 (± 14) days apart. The investigator will decide whether to continue treatment after each cycle based on the patient's state of health, and safety and efficacy assessments performed at the study centre.

Rollover EOS: The end of the rollover extension is defined as the last visit of the last patient. The end of study for the rollover extension for each individual patient will be their last rollover EOS, or death, whichever occurs earlier. At 90 (± 14) days after the last treatment cycle, patients will return to the study centre for the rollover EOS (see Table 10 of the current protocol. for assessments to be performed).

17.3.3 Rollover Study Visits and Time-Points

Safety and efficacy assessments will be performed as shown on Table 10 in the protocol. Study visit consists of screening/baseline, treatment cycle (pre-dose, PRRT, post-dose) and follow-up. The assessments will be conducted at the study centre according to local standards. As an exception only during the COVID-19 pandemic, if a patient is unable to attend his/her institutional site visit per the protocol schedule, blood samples may be collected and tested in the patient's local standards. However, the physical examination, vital signs, and ECG may be postponed to the next scheduled site visit. Any of these deviations from the protocol-specified schedule will be considered a minor protocol deviation. Assessments will be recorded in the eCRF. Patients enrolled in the rollover extension will simultaneously participate in the post-study follow-up for the main study (i.e. every 6 months for 5 years).

17.4 Handling of Missing Data

In general, unless otherwise specified, the handling strategy for all intercurrent events will be based on a treatment policy approach based on ICH E9 (R1). If possible, subjects will be followed up continuously and measurements will be collected continuously after the occurrence of the intercurrent event, until the subject either completes the study or withdraws from the study before completion. All subjects and measurements will be included in analysis.

Missing values will be treated as such, no imputation will be performed. The number of missing values will be reported. Missing information about tumour response at EOS will be censored on the day of the last available adequate assessment (See Section 17.8.2 for full censoring rule details for the rollover study).

